It is anticipated that all patients will be planned to receive 2 injections under this protocol, in order to allow dose-finding and to understand the duration of effect. Under certain circumstances a patient or investigator may decide to postpone or withhold the second dose. In general, if there appears to be any untoward safety risk, in situations including rapid deterioration of renal function, the development of uncontrolled diabetes, or the development of uncontrolled hypertension, or if there is the intercurrent development of a malignancy, the patient should not receive the second dose.

Second injections under this protocol will be staggered so that single injections in different patients occur no less than 3 weeks apart. The DSMB will review the clinical data regarding each of the first 3 second injections under this protocol, and will consult with the Sponsor before the 2nd, 3rd, and 4th second injections are made. Subsequent second injections will continue to be staggered so as to occur no less than 3 weeks apart, but individual DMSB review will not be required.

No staggering will be required for first NKA injections under this protocol.

Post-Injection Follow-up: Subjects will return to the clinic for follow-up safety assessments on Days 7, 14, and 28 post-injection and at 2, 3, and 6 months post-injection. At 6 months post-injection, post-treatment MRI and renal scintigraphy studies will be conducted. After patients complete the 6 month efficacy visit, they will be considered for a second NKA injection. Patients receiving a second dose will follow the same follow up visits that occurred after first injection. Patients 6 month post first injection visit will serve as the patients 14 to 10 day pre- second injection visit. Patients will return for their second injection and at 2, 3, and 6 months post-injection Patients will be followed up to 18 months in the post follow up phase with 6 months after first NKA injection and 12 months after second NKA injection. Refer to the time and events schedule on page 14 for additional post follow up time points.

Long Term Follow-up: Patients will be followed for safety and efficacy for 24 months after the 18 month initial follow up period. Telephone contact will be made 24 and 36 months after the last NKA injection, and visits will be made at 30 and 42 months after the last NKA injection.

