14.7 Safety Analysis

14.7.1 Biopsy, NKA Injection, Patient Disposition

Biopsy and NKA injection data will be provided in a data listing. Patient disposition (e.g., Screen Failure, Enrolled/Underwent Injection, Withdrawn Pre-injection, Successful injection, Discontinued Early Post-injection, Completed Study) will be summarized by frequency and proportion and will be provided in a data listing.

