14.7.2 Adverse Events

Clinical and laboratory AE's will be coded using the Medical Dictionary for Regulatory Activities (MedDRA). System Organ Class (SOC), High-Level Group Term (HLGT), High-Level Term (HLT), Preferred Term (PT), and Lower Level Term (LLT) will be attached to the clinical database. Adverse events will be graded using the NCI CTCAE scale.

A treatment-emergent AE will be defined as any adverse event that begins on or after the date of enrollment up to 18 months post-injection.

Summaries (frequency and proportion) of treatment-emergent AE's will be presented by SOC and PT.

Additional summaries will include, but are not limited to, treatment-emergent AE's by severity grade, Investigator's assessment of relationship to procedure and/or product, serious AE's (SAE's), related SAE's, and deaths. AE summaries will be provided for both the FAS and the Injection analysis set. There are no plans to generate inferential statistics. AE data will be provided in a data listing.

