14.8 Exploratory Analysis

As this study is a Phase II evaluation, hypothesis generating exploratory analyses may be conducted to help design future clinical studies. Subgroup analyses will compare patients receiving a single injection with patients receiving two injections, and patients receiving laparoscopic injections with patients receiving percutaneous injections.

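### The named adverse-event tables are not split by injection, so the planned summaries do not separate first- from second-injection risk, although the dated data would allow it

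*Combined protocol and SAP*

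**What the plan says.** Section 14.7.2 sets one window for all adverse events: "A treatment-emergent AE will be defined as any adverse event that begins on or after the date of enrollment up to 18 months post-injection". The main table follows: "Summaries (frequency and proportion) of treatment-emergent AE's will be presented by SOC and PT". Further tables cover severity, relationship, serious events, related serious events and deaths, for the Full Analysis Set and the Injection Analysis Set. None refers to the injection an event followed. The list is open, since it begins "Additional summaries will include, but are not limited to, treatment-emergent AE's by severity grade". No inferential statistics are planned for adverse events.

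On the underlying data, section 14.7.2 adds "AE data will be provided in a data listing", and section 14.7.1 says "Biopsy and NKA injection data will be provided in a data listing".

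The planned comparison bearing on re-injection is in section 14.8, and also in section 14.3 and the synopsis: "Subgroup analyses will compare patients receiving a single injection with patients receiving two injections". No outcome is named for it. A second subgroup comparison, laparoscopic versus percutaneous, does not bear on this point.

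The primary safety measure (section 14.3) counts related events through 12 months from the initial injection. New patients may receive two injections at least 6 months apart. Patients from the Phase 1 trials receive one here, their second overall. The synopsis says that the second dose should be withheld where there is a safety concern, including rapid renal deterioration, uncontrolled diabetes or hypertension, or malignancy. It also says: "The DSMB will review the clinical data regarding each of the first 3 second injections under this protocol".

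**The concern.** The primary objective covers safety and asks what two injections achieve. The protocol treats re-injection as a risk of its own: the synopsis staggers second injections and not first ones. Earlier patients are described as having had a single injection, and the repeat-dose animal evidence in section 6.3.3 is one study of eight dogs, including controls. Safety after a second injection is therefore one of the main things this trial can newly describe.

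A proportion of patients with an event at any time in the window merges both injections. A reader of the final tables could not tell whether events clustered after the first or the second. Returning patients, who contribute only a second lifetime injection, share the same denominator. If the tables are split only after the data are seen, the windows and denominators will also be chosen then.

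**Working it through.** The plan gives no event rate, power or sample-size calculation to reproduce. All rates below are assumed.

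**1. Pooling.** Let p1 and p2 be the risks after each injection, taken as independent. The proportion of two-injection patients with any event is 1 − (1 − p1)(1 − p2).
- 10% then 20%: 1 − 0.9 × 0.8 = 28%.
- 20% then 10%: 1 − 0.8 × 0.9 = 28%.
- Equal risks giving 28%: 1 − √0.72 = 15.1% each.

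The pooled table is the same whether risk doubles, halves or stays level.

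**2. One- versus two-injection patients.** Two distortions pull in opposite directions.
- More injections give more chances. With 10% after each injection and no extra re-injection risk, two-injection patients show 1 − 0.9 × 0.9 = 19% against 10% in one-injection patients.
- The rule for withholding the second dose leaves patients who did badly in the one-injection group, which could make two injections look safer.

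The text also does not say how returning patients are classed: they have one injection here and two in their lifetime.

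**3. The anchor.** The follow-up paragraph of section 9 describes 6 months after the first injection plus 12 after the second, 18 in all. The same section, section 11.4 and the schedule footnotes place the end-of-study visit 18 months after the second injection. Counted from the first injection, the window ends at 18 months; counted from the second, it ends about 24 months after the first (6 + 18).

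**4. Unequal exposure.** In an 18-month window from the first injection, about 6 months follow the first and 12 follow the second. At an assumed constant 3% per month:
- 6 months: 1 − exp(−0.18) = 16%.
- 12 months: 1 − exp(−0.36) = 30%.

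A split without equal windows would show nearly a doubling from time alone.

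**5. Unequal recording.** Section 13.3.1 records every event from injection to Month 12. From then to Month 18 it requires only related, severe or life-threatening, and CKD-related events. Section 11.4 puts the six-month visit within 3 days of six months and the second injection 10 to 14 days after that visit. The second injection thus falls about 7 days (10 − 3) to 17 days (14 + 3) after the six-month date. If Month 12 counts from the first injection, a six-month window after the second runs about 7 to 17 days past full recording, and further if the second dose is postponed.

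Serious events are less settled still. Section 13.3.2 has all of them recorded through the 6-month visit, while section 13.3.4 has them reported until the 18-month visit. If the 6-month visit is counted from the first injection, it precedes the second.

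**6. What a split can deliver.** At most 30 patients are injected, including up to 7 returning ones (six from Sweden, one from the US). That leaves at most 23 to 30 pairs, and only if every new patient is re-injected.
- Zero events: the exact two-sided 95% upper limit is 1 − 0.025^(1/30) = 11.6% for 30 second injections, or 1 − 0.025^(1/23) = 14.8% for 23.
- Exact two-sided McNemar power at 0.05, assuming independence:

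| First vs second | 30 pairs | 23 pairs |
|---|---|---|
| 10% vs 20% | 10% | 6% |
| 10% vs 30% | 36% | 24% |
| 10% vs 40% | 68% | 52% |
| 20% vs 40% | 28% | 20% |

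**The case against.** The strongest reply is that nothing is lost. The list of summaries is open, events and injections are both listed, and section 14.8 allows further exploratory work. With at most 30 patients a by-injection table could be made under the present text. No stated objective compares the two injections, and the primary safety measure is cumulative by design.

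Much of this stands, and it rules out some stronger readings. A reader might infer that the trial cannot show whether re-injection carries more risk. The documents do not support that: the gap is in the named tables, not in the data. Nor do they support the inference that re-injection decisions rest on the pooled table. The DSMB reviews the first three second injections individually, product-related events are forwarded to it (section 13.5), listed events halt further injections pending its review (section 13.6), and each patient's second dose depends on that patient's condition.

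A reader might also infer that splitting the tables would expose a doubling of risk. The power figures say otherwise. Nor are the pairs a clean contrast: they are selected for having tolerated the first injection, and the disease is at a later stage by the second.

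What the reply does not meet is that permission is not a plan. Unequal follow-up and narrowing event recording mean that the windows and denominators need fixing in advance.

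**Conclusion.** The concern holds for the planned summaries. The tables named in section 14.7.2 do not separate first- from second-injection risk, and the one- versus two-injection comparison does not fill the gap, because it is between patients selected by how they fared after the first injection.

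The effect is on what the final safety tables can say, not on patient oversight during the trial. The 28% illustration rests on assumed, independent risks. That a split can be built rests on event onset dates being held, which is inferred from the onset-based definition of a treatment-emergent event. The gain is descriptive: a by-injection count with its own denominator, and for instance an upper limit of 11.6% if none of 30 second injections is followed by a given event. It would not support a reliable test.

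**What to change.** In section 14.7.2:

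- State which injection anchors the treatment-emergent window.
- Add descriptive summaries of all, serious, related and special-interest events by most recent injection, with patients given that injection as denominator.
- Put returning Phase 1 patients in their own column, and show paired first/second counts for patients given both injections here.
- Use equal windows within which recording is the same: for example 28 days, plus a longer window that ends before the next injection and before recording narrows at Month 12. Alternatively, keep a six-month window but limit it to categories recorded throughout: product- or procedure-related, severe or life-threatening, and CKD-related.
- State that the comparison is descriptive and that no test is planned.

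Separately, reconcile the serious-event recording period in section 13.3.2 with the reporting period in section 13.3.4, and say from which injection each visit is counted.

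The cost is some table programming. With windows chosen this way, the tables ask sites for no event recording beyond section 13.3.1; reconciling the serious-event periods may clarify what they record.

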14.7.3 Laboratory Evaluations

Baseline values will be collected immediately prior to injection. Observed and change from baseline laboratory data will be summarized using a typical 8-number summary (sample size, mean, standard deviation, median, Q1, Q3, minimum, and maximum) for continuous variables and frequency and proportion for categorical variables. These summaries will be produced for both the FAS and the Injection analysis set. Generating inferential statistics is not planned.

Graded laboratory abnormalities will be defined using the NCI CTCAE grading scheme as defined in Section 12.3. Incidence of treatment-emergent laboratory abnormalities, defined as values that increase at least 1 toxicity grade from baseline at any time post baseline up to six months post-injection will be summarized. If baseline data are missing, then the latest value collected between biopsy and injection will be used as the baseline value. If baseline and pre-injection data are missing, then any graded abnormality, i.e., at least a Grade 1, will be considered treatment emergent.

Laboratory data summaries will be provided for both the FAS and the Injection analysis set. There are no plans to generate inferential statistics, except for variables concerning the rate of renal insufficiency progression. A paired t-test may be performed to assess the change in the rate of progression of renal insufficiency. Laboratory data will be provided in a data listing.

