Discharge: After an injection via the percutaneous route, the patient may be discharged the same day if that is the site's usual practice after similar procedures (i.e. percutaneous ablation), after no less than 2 hours of observation and monitoring. If product- or procedure-related AE's occurred following surgery, the patient should not be released from the hospital until the AE's have either resolved, stabilized, or returned to baseline. After a laparoscopic injection, the patient should be observed in hospital for 2 to 4 nights to assess for AEs.

11.4 Follow-up (Days 7, 14, and 28, 2month, 3month, 6month ± 3 days first injection and second injection)

The patient should return to the clinic for follow-up visits one week after injection (Day 7) and on Days 14 and 28. The patient should make every attempt to return for the first follow-up visit on the protocol-specified day (i.e., Day 7) although a 3 day window will be allowed in the case of extenuating circumstances. A 3-day window is allowable for visits on Days 14 and 28, and on Months 2, 3, 6, and 12. At Month 6 visit the same procedures as the pre-injection visit should occur to prepare for the second injection of NKA, if the patient and investigator wish to proceed. The month 6 visit should occur -14 to -10 days before second injection and within 3 days of 6 months post first injection. Patients will return to the clinic Days 7, 14, and 28 after second injection and Months 2, 3, 6, 9, and 12 after second injection.

The monthly visit dates should be calculated using the calendar date of injection. For example, if the patient was injected on April 30^{th} , then the protocol-specified date of the 2 month follow-up visit would be June 30^{th} and the 3 month visit date would be July 30^{th} , etc. The visit window for the long-term monthly follow-up visits is ± 7 days.

End-of-Study Visit (EOS): Patients will complete the EOS Visit as noted below:

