14.3 Endpoints

The primary endpoint of the study is to assess the safety and efficacy of NKA injected in one recipient kidney and determine if two injections of NKA provide stabilization of renal function.

- Primary Safety Outcome Measures: procedure and/or product related adverse events (AE's) through 12 months following the initial NKA injection.
- Primary Efficacy Outcome Measures: serial measurement of serum creatinine and estimation of GFR through 6 months following the second cell injection

Secondary Endpoint

The secondary endpoint of the study is to assess the safety and tolerability of NKA administration by assessing renal-specific adverse events over a 12 month period following a patient's first NKA injection.

• Secondary Safety and Tolerability Outcome Measures: renal-specific laboratory assessments through 12 months following the last NKA injection under this protocol, whether first or second.

Exploratory Endpoints

The exploratory endpoint of the study are designed to assess the impact of NKA on renal function over a 12 month period following the initial NKA injection.

• Exploratory Outcome Measures: clinical diagnostic and laboratory assessments of renal structure and function (including eGFR, serum creatinine, and proteinuria) to assess changes in the rate of progression of renal disease; and effect of method of injection on these parameters.

Exploratory quality of life outcome measure will be the Kidney Disease Quality of Life survey obtained at baseline and at 1, 3, 6, 7, 9, 12, 15, 18, 30, and 42 months after a patient's first NKA injection.

- Changes from baseline in BUN, $_{\beta}2$ microglobulin and intact parathyroid hormone (iPTH) at 6 and 12 months post-injection.
- Changes from baseline in C-reactive protein (CRP) at 6 and 12 months post-injection.
- Need for initiation of renal replacement therapy.
- Comparison of pre-injection versus post-injection split functional differences between the left and right kidney based on renal scintigraphy.
- Comparison of pre-injection and post-injection kidney volume estimates based on comparative MRI assessments.
- Subgroup analyses will compare patients receiving a single injection with patients receiving two injections, and patients receiving laparoscopic injections with patients receiving percutaneous injections.

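### The treatment-emergent graded laboratory table in 14.7.3 stops six months after an unnamed injection, while the secondary laboratory outcome measure runs to 12 months after the last injection

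*Combined protocol and SAP*

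**What the plan says.** **Graded laboratory table.** Section 14.7.3 defines a treatment-emergent laboratory abnormality as a rise of at least one toxicity grade from baseline "at any time post baseline up to six months post-injection will be summarized". On baseline it says: "Baseline values will be collected immediately prior to injection". Neither sentence names the first or the second injection. The other laboratory summaries in the section carry no end date: "Observed and change from baseline laboratory data will be summarized using a typical 8-number summary". The listing has none either.

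**Secondary outcome.** The synopsis and Sections 7.1, 14.2 and 14.3 give the secondary outcome measure as "renal-specific laboratory assessments through 12 months following the last NKA injection under this protocol", whether that is the first or the second. The sentence just before it words the secondary objective (endpoint, in 14.3) differently: renal-specific adverse events over 12 months from the first injection.

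**Timing of the second injection.** The injections must be at least 6 months apart. Section 11.4 says "The month 6 visit should occur -14 to -10 days before second injection" and within 3 days of 6 months after the first. Visits then follow on Days 7, 14 and 28 and at "Months 2, 3, 6, 9, and 12 after second injection". The synopsis adds: "Under certain circumstances a patient or investigator may decide to postpone or withhold the second dose".

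**SAE recording (minor note).** Section 13.3.2 puts all SAEs on the CRF through a 6-month visit that it does not tie to an injection, and after that only product-related SAEs in the long-term phase. Section 13.3.4 has all SAEs reported to the sponsor until the 18-month visit. Section 14.7.2 defines treatment-emergent events to 18 months.

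**The concern.** The primary objective asks whether two injections stabilize renal function, and Sections 14.3 and 14.8 plan to compare one injection with two. The graded table is the only planned laboratory display that counts patients whose toxicity grade worsened. With the injection unnamed, two programmers could follow the text and build different tables. One of those tables would hold nothing after the second injection. On any choice of injection, the table ends before the secondary laboratory outcome measure does.

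The baseline has the same gap. The value before the first injection is a usable reference, but on its own it cannot separate a shift that arose after the second injection from one already present before it.

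**Working it through.** **The plan's own figure.** The synopsis and Section 9 build the initial follow-up as 6 months after the first injection plus 12 months after the second: 6 + 12 = 18 months. This reproduces.

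**Inputs.** 6 months = 183 days and 12 months = 365 days; Day 0 is the first injection under this protocol. Section 11.4 puts the Month 6 visit within 3 days of 6 months, and the second injection 10 to 14 days after that visit.

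**On-schedule second injection, S.**
- Earliest: 183 − 3 + 10 = Day 190.
- Latest: 183 + 3 + 14 = Day 200.

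**End of the secondary laboratory measure.**
- One injection: Day 365.
- Two injections: S + 365 = Day 555 to 565.

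**Scheduled outpatient laboratory visits.**
- After a second injection, the laboratory schedule has 8: Days 7, 14 and 28, then Months 8, 9, 12, 15 and 18.
- After a single injection, there are 8 to Month 12: Days 7, 14 and 28, then Months 2, 3, 6, 9 and 12.

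**Shortfall = end of secondary measure − end of table.**

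| Case | Table ends | Measure ends | Shortfall | Visits kept |
|---|---|---|---|---|
| One injection | Day 183 | Day 365 | 182 days (6.0 months) | 6 of 8 |
| Two, counted from each or the last | S + 183 = Day 373 to 383 | Day 555 to 565 | 182 days (6.0 months) | 6 of 8 after the second |
| Two, counted from the first | Day 183 | Day 555 to 565 | 372 to 382 days (12.2 to 12.6 months) | 0 of 8 after the second |

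Months are days × 12/365. In the second row the omitted visits are Months 15 and 18. On the Section 11.4 visit list they are Months 9 and 12 after the second injection, and the count is again 6 of 8.

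**Sensitivity to timing.** The third row does not depend on the day arithmetic. With at least 6 months between injections, a six-month window from the first cannot cover follow-up after the second. If the second is postponed, only this row grows. At an assumed spacing of 9 months the measure ends at 9 + 12 = 21 months and the shortfall is 21 − 6 = 15 months.

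**Against the other horizon in 14.3.** Twelve months after the first injection is Day 365. A table counted from the last of two injections ends on Day 373 to 383, which is 8 to 18 days later, so it is not short. A table for one injection, or counted from the first of two, is short by 365 − 183 = 182 days.

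**SAE recording, sections read together.**
- Section 13.3.1 takes any AE to Month 12. From Month 12 to 18 it takes AEs that are related, severe or life-threatening, or CKD-related, and exempts the rest unless the investigator decides otherwise.
- This leaves unrelated, non-severe, non-CKD SAEs in Months 12 to 18. Section 13.3.4 requires them to be reported; 13.3.1 exempts them from the CRF; 13.3.2 is silent.
- Three other texts point towards recording them without fully closing the gap: 13.1.1 (all AEs on the AE CRF), 13.3.3 (SAEs found at the last scheduled visit) and the part of 13.3.4 on competent authorities (timely eCRF entry).

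**The case against.** **The table is not declared to be the secondary analysis.** This is correct. It covers all graded laboratory results, while the secondary measure is renal-specific. A 12-month window for this table is therefore a matter of consistency with the outcome measure, not a stated requirement. The unnamed injection is a defect either way.

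**The secondary endpoint is also worded as 12 months from the first injection.** This stands too. On that horizon a table counted from the last of two injections is long enough. It does not help a patient with one injection, or a table counted from the first of two.

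**Late abnormalities have another route.** Under 13.1.1 a laboratory finding becomes an AE if it is judged clinically significant, involves therapeutic intervention or leads to discontinuation. Section 13.3.1 names a clinically significant rise in serum creatinine as recordable in Months 12 to 18, and 14.7.2 tabulates laboratory AEs by grade to 18 months. This reduces the harm. It does not replace the table, because a one-grade shift that meets none of those conditions is not counted there.

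**Stronger readings that the documents do not support.** A reader might infer that the secondary laboratory outcome goes unanalysed after six months. It does not: the 8-number summaries and the listing have no cut-off. A reader might also infer from 13.3.2 that SAEs after Month 6 are lost. They are not: 13.3.1 records any AE to Month 12, and 13.3.4 sends all SAEs to the sponsor until the 18-month visit.

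**Conclusion.** The point holds for one table and should be fixed before the tables are programmed. The treatment-emergent graded laboratory incidence ends 6 months before the secondary laboratory outcome measure for one injection, and for two if counted from each or the last. It ends about 12 months before it, with 0 of 8 visits after the second injection, if counted from the first. The figures assume an on-schedule second injection and the outcome-measure wording in 14.3, not the alternative horizon of 12 months from the first injection. The effect is an ambiguous and shortened display, not lost laboratory data.

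The SAE mismatch is a minor note. It concerns CRF recording of one class of event in Months 12 to 18 that still reaches the sponsor, so the risk is that the CRF-based SAE tables and the safety database disagree.

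The 18-month visit also has two meanings. Section 9 contains both the 6 + 12 month construction and an End-of-Study visit 18 months after the second injection. Section 11.4 ends its visit list at Month 12 after the second injection, yet places End of Study at 18 months after it.

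**What to change.** **Section 14.7.3.**
- Count graded abnormalities through 12 months after the last NKA injection under this protocol. State this as time since that injection, not as Month 18, because Month 18 has two meanings.
- Keep the value before the first injection under this protocol as the main baseline.
- Add a display by injection, with the last value before the second injection as its reference.

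**Sections 13.3.1 and 13.3.2 (minor).** Align the CRF recording period for SAEs in 13.3.2 with the reporting period in 13.3.4, and take SAEs out of the exemption for other AEs in 13.3.1.

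**Sections 9 and 11.4.** Reconcile the two meanings of the 18-month visit, and carry the result into the schedule footnotes and every window that uses it.

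**Cost.** Wording changes and some table programming. No new samples: the laboratory schedule already has chemistry on the day of the second injection, hematology at the Month 6 pre-injection visit, and both at the later visits to Month 18. CRF entry of the residual SAEs is a small task, since they are already reported. One drawback is that later graded abnormalities may reflect CKD progression, and the table should say so.
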